8.4.4. Clinical Safety Laboratory Tests

Routine blood and urine samples for laboratory assessments will be collected at the visits specified in the SoA in [Section 1.3](#). The Investigator will receive the results of this testing from the Central Laboratory and must determine the clinical significance of any results that are outside of the normal range. All patients with clinically significant abnormal test results will be followed regularly until the values return to normal ranges, until a valid reason other than study intervention related AE is identified, or until further follow-up is deemed medically unnecessary.

Full instructions concerning the number and type of laboratory samples to be collected at each visit, the necessary collection supplies, required sample volumes, sample collection methods, sample processing, sample labeling, and sample shipping will be provided by the Central Laboratory and will be appropriately assembled for the specific evaluations required at each visit.

- See [Section 10.3](#) for the list of clinical laboratory tests to be performed and the SoA (Section 1.3) for the timing and frequency.
- The Investigator must review the laboratory results, document this review, and record any clinically significant changes occurring during the study as an AE. The laboratory results must be retained with source documents.
- All laboratory tests with values considered clinically significantly abnormal during participation in the study or until EOS should be repeated until the values return to normal or baseline or are no longer considered clinically significant by the Investigator or Medical Monitor.
- If clinically significant values do not return to normal/baseline within a period of time judged reasonable by the Investigator, the etiology should be identified, and the Sponsor notified.
- All protocol-required laboratory tests, as defined in Section 10.3, must be conducted in accordance with the laboratory manual and the SoA (Section 1.3).
- If laboratory values from non-protocol-specified laboratory tests performed at the institution's local laboratory require a change in participant management or are considered clinically significant by the Investigator (eg, SAE or AE or dose modification), then the results must be recorded.

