10.8. Appendix 8: Recommendations for Management of Hyperkalemia

Serum potassium checks should be completed at each visit for clinical evidence of electrolyte imbalance. If a patient has a serum potassium value of >5.5 mEq/L (5.5 mmol/L) at any time during the study, the following steps are recommended:

1. If the serum potassium value is ≥ 6.5 mmol/L, emergency management should be implemented based on the site policies and Investigator's decision.
2. If the serum potassium value is >5.5 and <6.5 mmol/L, rule out measurement errors or likely reasons for the increase (eg, sample hemolysis, metabolic acidosis, discontinuation of diuretic by the patient/lack of compliance, diet transgression).
 - a. If the causes listed above are ruled out and the patient is not receiving a diuretic, it is recommended to start a diuretic (if the patient's volume status and BP permit). The choice of a thiazide or a loop diuretic is at the discretion of the Investigator. Assess the patient's tolerability and measure their BP, eGFR, sodium, and potassium within 1 week after starting the diuretic.
 - b. If the causes listed above are ruled out and the patient is already receiving a diuretic, increase the dose of the diuretic by 50% (if the patient's volume status and BP permit). Assess the patient's tolerability and measure their BP, eGFR, sodium, and potassium within 1 week after increasing the dose. Consider correction of metabolic acidosis, if relevant.
3. In both scenario 2a and 2b, adjust the dose of diuretic accordingly after 1 week. If the patient's serum potassium value is still >5.5 mEq/L (5.5 mmol/L), reinforce diet counseling/restrictions, rule out other potential causes of hyperkalemia, and consider increasing the diuretic dose. If, after an additional week, the serum potassium value is still >5.5 mEq/L (5.5 mmol/L), reduce the dose of study intervention by 50%. For long-term prevention of hyperkalemia, consider treatment with patiromer or sodium zirconium cyclosilicate.
4. If hyperkalemia persists or recurs, study intervention must be discontinued permanently.

10.9. Appendix 9: Liver Safety: Suggested Actions and Follow-up Assessments and Study Intervention Rechallenge Guidelines

Abnormal liver function test results that meet at least one of the following criteria below will be considered AEOIs and must be reported to the Sponsor's Medical Monitor within 24 hours of awareness:

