- The abnormality represents a new elevation in ALT or AST >3 times ULN, with or without an elevation of total serum bilirubin >2 times ULN.
- The abnormality represents a 2-fold increase in ALT or AST above the baseline value for the study period (ie, Day 1) in participants who had elevated values prior to starting study intervention.

In such instances, the following steps should be taken:

1. Temporarily discontinue study intervention.
2. Perform repeat testing of ALT, AST, liver specific alkaline phosphatase (ALP), and total bilirubin within 48 to 72 hours to confirm the abnormalities.
3. If the abnormality is confirmed by repeat results, the following should be done:
 - a. Complete an AEOI Report Form that documents both the liver function test findings and any associated signs or symptoms, and report by email to the SAE contact on the SAE Contact Information page ([Section 10.1.1](#)) of this protocol.
 - b. Monitor liver enzymes and serum bilirubin 2 or 3 times weekly. The frequency of retesting can decrease to once weekly or less if the abnormalities stabilize and the participant is asymptomatic.
 - c. Perform additional testing to evaluate liver function, as appropriate (eg, INR and direct bilirubin).
4. Do not resume study intervention until monitoring indicates abnormalities have resolved or stabilized.

Participants are not allowed to resume study intervention if they have the following:

- ALT or AST >8 times ULN.
- ALT or AST >5 times ULN for more than 2 weeks.
- ALT or AST >3 times ULN and total bilirubin >2 times ULN or INR of >1.5 .
- ALT or AST >3 times ULN, with symptoms of fatigue, nausea, vomiting, right upper quadrant pain or tenderness, fever, rash, and/or eosinophilia ($>5\%$ eosinophils).

Management of such participants should be closely coordinated with the Sponsor's Medical Monitor. In addition to monitoring liver function tests, the Investigator should perform other relevant clinical and laboratory measurements to identify potential causes of the abnormalities (eg, acute viral hepatitis types A, B, C, D, and E; autoimmune or alcoholic hepatitis; nonalcoholic steatohepatitis; biliary tract disease or exposure to hepatotoxic medications or environmental chemical agents). Additionally, participants who demonstrate elevated liver enzymes a second time after re introduction of the study intervention may continue in the clinical study; however, they will not receive study intervention for the remainder of the trial.

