### 6.5.3. Visit Windows

A visit window method will be applied to determine the record to be used for analysis across the study period for efficacy and safety endpoints based on laboratory results, including eGFR and quantitative urinalysis (including UP/C and UA/C). If a patient has multiple assessments (including unscheduled visits) within the visit window, the value closest to the target day for that visit will be selected for analysis. If more than 1 assessment is equidistant to the target day, then latest value will be selected.

The visit window shown in Table 1 is defined for endpoints based on laboratory results.

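### The SAP visit-window rule lets an unscheduled retest displace the scheduled laboratory value that prompted it, so by-visit safety-lab and eGFR summaries lean slightly toward recovery (minor)

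*Protocol*

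**What the plan says.** Protocol 8.4.4 (Clinical Safety Laboratory Tests) says that tests with clinically significant abnormal values "should be repeated until the values return to normal or baseline", or until the Investigator or Medical Monitor no longer judges them clinically significant. Two appendices add specific retests. Appendix 8 (hyperkalemia) tells the site to "measure their BP, eGFR, sodium, and potassium within 1 week after starting the diuretic", and likewise after a diuretic dose is increased. Appendix 9 (liver safety), after a temporary hold of study intervention, says "Perform repeat testing of ALT, AST, liver specific alkaline phosphatase (ALP), and total bilirubin within 48 to 72 hours".

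SAP 6.5.3 (Visit Windows) covers efficacy and safety endpoints based on laboratory results, eGFR included. "If a patient has multiple assessments (including unscheduled visits) within the visit window", then "the value closest to the target day for that visit will be selected for analysis". On ties: "If more than 1 assessment is equidistant to the target day, then latest value will be selected". SAP Table 1 has a column for eGFR and safety labs. No text gives the scheduled sample priority.

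The selected values feed the by-visit laboratory summaries (SAP 9.5) and the eGFR summaries and MMRM (SAP 8.2.2.2).

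**The concern.** A clinically significant abnormal scheduled result leads to a retest; a normal one does not under these rules. If the retest can take the scheduled sample's place, the value analysed at that visit depends on what the first value was. A value picked out for being extreme tends to be less extreme when repeated, and some retests follow treatment or a hold of study drug. By-visit summaries would then tend to understate acute changes at the visit where they occurred.

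This matters most for eGFR. Protocol Table 1 says the combination with an SGLT2 inhibitor may raise the risk of acute kidney injury. Yet SAP 9.1.2 lists no kidney-injury topic and the SAP has no table of eGFR decline by threshold. By-visit eGFR is therefore one of the main displays of an acute fall, alongside the serum chemistry shift tables.

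**Working it through.** **The plan's own figure.** The only design figure is the chance of seeing at least one event at 5% incidence with 60 participants: 1 - 0.95^60 = 0.954, which agrees with the stated 95%. The point below does not depend on it.

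**Inputs from the documents.** Target days 15, 29, 85 and 169, with eGFR and safety-lab windows 2-22, 23-57, 58-127 and 128-183 (SAP Table 1). Allowed visit deviation of 5 days at Week 2 and 7 days at Weeks 4, 12 and 24 (Protocol 1.3). Retest delays of 48-72 hours (Appendix 9) and within 1 week of a diuretic change (Appendix 8).

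**Assumed.** Scheduled days are uniform over the allowed range. Delays of 10 and 14 days are added because central-laboratory turnaround is not stated.

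**When the repeat wins.** Let the scheduled sample be e days before target and the repeat k days later. The repeat is |k - e| days from target. It is selected when |k - e| <= e, that is when k <= 2e, or e >= k/2; equality is a tie and goes to the later sample. If the scheduled sample is on or after target, the repeat is further away and never wins.

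**Examples.** A Week 12 visit on Day 80 with a repeat on Day 87 is 5 days against 2, so the repeat is selected. A visit on Day 83 with a repeat on Day 90 is 2 against 5, so the scheduled value stays. At Week 24, Days 164 and 174 are both 5 days from Day 169, so the repeat is selected.

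**Counts of allowed visit days on which the repeat replaces the scheduled value.**

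| Delay k (days) | Smallest e | Week 2 (of 11) | Week 4 (of 15) | Weeks 12 and 24 (of 15 each) |
|---|---|---|---|---|
| 2 | 1 | 5 (45%) | 6 (40%) | 7 (47%) |
| 3 | 2 | 4 (36%) | 5 (33%) | 6 (40%) |
| 5 | 3 | 3 (27%) | 4 (27%) | 5 (33%) |
| 7 | 4 | 2 (18%) | 3 (20%) | 4 (27%) |
| 10 | 5 | 1 (9%) | 2 (13%) | 3 (20%) |
| 14 | 7 | 0 | 0 | 1 (7%) |

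Week 4 has one day fewer because an allowed visit on Day 22 falls in the Week 2 window. If visits cluster around target (triangular instead of uniform), Weeks 12 and 24 give 44%, 33%, 16% and 2% for k = 2, 3, 7 and 14.

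**Shift in mean eGFR at a visit** = share flagged x probability of replacement x mean rebound. The documents give none of these, so ranges are assumed: 2-10% flagged, 7-40% replaced, rebound 3-10 mL/min/1.73 m2.
- Low: 0.02 x 0.07 x 3 = 0.004
- Middle: 0.05 x 0.27 x 5 = 0.07
- High: 0.10 x 0.40 x 10 = 0.40 (0.47 if 47% are replaced)

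For scale, the standard error of a mean change with n = 60 is 6/sqrt(60) = 0.8 to 10/sqrt(60) = 1.3, if the SD is 6-10 (assumed).

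**Check without any true recovery.** A simulation took true changes with mean -2 and SD 5, measurement SD 3 or 5, retests for falls beyond 10, and 4/15 replaced. It flagged 8.5% or 12.9%, with mean rebounds of 2.8 or 5.8, and moved the mean by 0.06 or 0.20. Regression to the mean alone gives the average pull.

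**Week 24 eGFR.** SAP 8.1 counts an efficacy value as on treatment only up to 3 days after the last dose. If dosing ends at the Week 24 visit, a repeat later than that cannot enter. Safety-lab tables have no such limit, and neither would the optional repeat analysis on all on-study data. Before Week 24, a repeat during a temporary hold still counts, because the cut-off runs from the last dose.

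**The case against.** The case against giving this weight is substantial.

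- **Repeat until normal.** A reader might infer that abnormal tests must be repeated until they normalise. Protocol 8.4.4 is worded as a recommendation, allows stopping once the value is no longer clinically significant, and lets follow-up end for other stated reasons. Nothing in 8.4.4 is itself defective; the issue lies in SAP 6.5.3.
- **One direction only.** A reader might infer that replacement always favours recovery. The rule keeps the sample nearest to target, not the last or the normalised one. A 48-72 hour liver repeat is meant to confirm the abnormality and may be as bad or worse. The eGFR repeat in Appendix 8 is prompted by potassium, not by a low eGFR, and follows a diuretic change, so that route does not by itself imply an upward pull. What stands is an average tendency.
- **Any early visit.** Replacement needs a visit at least half the retest delay early. The scheduled value survives in 53-82% of cases at 2-7 days, and in more at longer delays. Results must first come back from the central laboratory, so longer delays are plausible.
- **Central laboratory only.** SAP 6.6.2 and 8.1 keep local repeats out of the primary analyses. This limits the effect, though the optional analysis adding local data (SAP 8.2.4) would widen it.
- **Scheduled visits in SAP 9.5.** That section summarises by scheduled visit, which might be read as excluding unscheduled samples. But SAP 6.5.3 expressly applies its rule to safety laboratory endpoints, and 9.5 claims no exemption.
- **Signal retained.** Worst-value normal-range and CTCAE shifts, liver-threshold counts, adverse event records and listings keep the triggering value. By-visit and worst-value tables answer different questions, so a difference between them is not an error.

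These points reduce the size of the problem. None gives the scheduled sample priority.

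**Conclusion.** The mechanism is real: SAP 6.5.3 makes the value analysed at a visit depend partly on whether the scheduled result was abnormal. Under uniform visit days, a central-laboratory repeat displaces the triggering value in about 18-47% of flagged cases at 2-7 days and 0-20% at 10-14 days. The pull toward recovery holds on average only.

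The consequence is small. The shift in mean eGFR is about 0.004-0.4 mL/min/1.73 m2, with a middle case of 0.07, well below an assumed standard error of 0.8-1.3. The flagged share, rebound, SD, visit-day distribution and longer delays are assumptions.

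The documents do not support reading this as a loss of safety signals or as a material bias in the Week 24 on-treatment eGFR estimate, which the 3-day rule largely protects. Nor is the point extended to UA/C, since the specific retest instructions concern liver tests, potassium and eGFR. The study is descriptive, with no efficacy hypothesis. Severity: minor, but worth correcting because the correction is cheap.

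**What to change.** In SAP 6.5.3, select the scheduled-visit central-laboratory sample whenever one lies in the analysis window. Use an unscheduled sample only if no scheduled sample is in the window or the central laboratory invalidated it; then take the one closest to target, with ties to the earliest. Leave the worst-value, threshold and listing outputs unchanged.

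A valid scheduled sample in its window can then no longer be displaced by its own retest. One edge case remains: a Week 4 visit on Day 22 falls in the Week 2 window, so a retest from Day 23 could still stand as the Week 4 value. Starting the Week 4 eGFR and safety-lab window at Day 22 would close this, since Day 22 is 7 days from both targets and Week 2 visits are allowed only to Day 20.

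The cost is two sentences and a small programming change, with no new data and no change to any clinical rule. The downside is that the chosen sample may lie a few days further from the target day.

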8.4.5. Pregnancy Testing

Participants who can become pregnant, as defined in [Section 10.7](#), must not become pregnant. Acceptable forms of contraception are also defined in Section 10.7.

At screening, serum pregnancy tests will be performed on participants who can become pregnant. Urine pregnancy tests will be performed at all other visits and monthly between visits. Urine pregnancy tests will be dispensed to participants who can become pregnant to conduct pregnancy testing at home once per month until the next scheduled study visit. If the urine pregnancy test is positive, study intervention will be immediately discontinued, and a serum

pregnancy test will be performed to confirm the result. If the serum pregnancy test is positive, the Sponsor will be notified, and the participant will be followed to pregnancy outcome as outlined in [Section 8.5.5](#).

- Refer to [Section 5.1](#) Inclusion Criteria for pregnancy testing entry criteria.
- Pregnancy testing (urine or serum as required by local regulations) is to be conducted every 4 weeks during intervention.
- Pregnancy testing (urine or serum as required by local regulations) should be conducted at the end of relevant systemic exposure and correspond with the time frame for contraception in [Section 5.1](#) Inclusion Criteria.
- Additional serum or urine pregnancy tests may be performed, as determined necessary by the Investigator or required by local regulation, to establish the absence of pregnancy at any time during the participant's participation in the study.

8.4.6. Suicidal Ideation and Behavior Risk Monitoring

No known risk of suicidal ideation associated with the use of sparsentan. If suicidal ideation and/or behavior risk monitoring is to occur, participant should refer to mental health services.

8.5. AEs SAEs, and Other Safety Reporting

The participant will be evaluated for new AEs and the status of existing AEs per the SoA ([Section 1.3](#)) and any time contact is made with the participant outside of a scheduled visit.

The definitions of AEs and SAEs can be found in [Section 10.5](#).

The Investigator and any qualified designees are responsible for detecting, documenting, and recording events that meet the definition of an AE or SAE and remain responsible for following up AEs that are serious, considered related to the study intervention or study procedures, or that caused the participant to discontinue the study intervention or study (see [Section 7](#)). This includes events reported by the participant (or, when appropriate, by a caregiver, surrogate, or the participant's legally authorized representative).

The method of recording, evaluating, and assessing causality of AEs and SAEs and the procedures for completing and transmitting SAE reports are provided in [Section 10.5](#).

8.5.1. Time Period and Frequency for Collecting AE and SAE Information

All AEs will be collected from the signing of the ICF until the follow-up visit at the timepoints specified in the SoA ([Section 1.3](#)).

All SAEs will be recorded and reported to the Sponsor or designee immediately and under no circumstance should this exceed 24 hours, as indicated in [Section 10.5](#). The Investigator will submit any updated SAE data to the Sponsor within 24 hours of it being available.

Investigators are not obligated to actively seek information on AEs or SAEs after conclusion of the study participation. However, if the Investigator learns of any SAE, including a death, at any time after a participant has been discharged from the study, and the Investigator considers the event to be reasonably related to the study intervention or study participation, the Investigator must promptly notify the Sponsor.

8.5.2. Method of Detecting AEs and SAEs

Care will be taken not to introduce bias when detecting AEs and/or SAEs. Open-ended and nonleading verbal questioning of the participant is the preferred method to inquire about AE occurrences.

8.5.3. Follow-up of AEs and SAEs

After the initial AE/SAE report, the Investigator is required to proactively follow each participant at subsequent visits/contacts. All SAEs and AEs of special interest (as defined in [Section 8.5.7](#)) will be followed until resolution, stabilization, the event is otherwise explained, or the participant is lost to follow-up (as defined in [Section 7.3](#)). Further information on follow-up procedures is provided in [Section 10.5](#).

8.5.4. Regulatory Reporting Requirements for SAEs

- Prompt notification by the Investigator to the Sponsor of an SAE is essential so that legal obligations and ethical responsibilities towards the safety of participants and the safety of a study intervention under clinical investigation are met.
- The Sponsor has a legal responsibility to notify both the local regulatory authority and other regulatory agencies about the safety of a study intervention under clinical investigation. The Sponsor will comply with country-specific regulatory requirements relating to safety reporting to the regulatory authority, IRBs/IECs, and investigators.
- An Investigator who receives an Investigator safety report describing an SAE or other specific safety information (eg, summary or listing of SAEs) from the Sponsor will review and then file it along with the Investigator's Brochure/Investigational Directions for Use (IDFU)/package insert and will notify the IRB/IEC, if appropriate according to local requirements.
- Investigator safety reports must be prepared for suspected unexpected serious adverse reactions (SUSARs) according to local regulatory requirements and Sponsor policy and forwarded to investigators as necessary.

8.5.5. Pregnancy

- Details of all pregnancies in participants will be collected after the start of study intervention and until 90 days following the final dose of study intervention.
- If a pregnancy is reported, the Investigator will record pregnancy information on the appropriate form and submit it to the Sponsor within 24 hours of learning of the participant's pregnancy.
- While pregnancy itself is not considered to be an AE or SAE, any pregnancy complication or elective termination of a pregnancy for medical reasons will be reported as an AE or SAE.
- Abnormal pregnancy outcomes (eg, spontaneous abortion, fetal death, stillbirth, congenital anomalies, ectopic pregnancy) are considered SAEs and will be reported as such.

- The participant will be followed to determine the outcome of the pregnancy. The Investigator will collect follow-up information on the participant and the neonate, and the information will be forwarded to the Sponsor.
- Any poststudy pregnancy-related SAE considered reasonably related to the study intervention by the Investigator will be reported to the Sponsor as described in [Section 8.5](#). While the Investigator is not obligated to actively seek this information in former study participants, he or she may learn of an SAE through spontaneous reporting.
- Any participant who becomes pregnant while participating in the study will discontinue study intervention.

Participants will be instructed to discontinue study intervention and to notify the Investigator immediately if they discover they are pregnant. If the Investigator learns of a report of pregnancy after signing informed consent, the Investigator will complete the pregnancy forms and submit them to the study contact on the Study Contact Information page ([Section 10.1.1](#)) of this protocol or by fax to the number in the Investigator Site File.

All pregnancies in participants will be followed to outcome (ie, delivery, elective termination, spontaneous abortion). Infants should be followed for a minimum of 8 weeks. In certain cases, it may be necessary to follow-up on the long-term outcome of the AE using the pregnancy follow-up form. The Investigator will inform the participant that the Sponsor or its designee is required to gather information regarding the course and outcome of the pregnancy after exposure to the study intervention. All study-related visits/contacts involving a known pregnancy will include pregnancy status assessment until pregnancy outcome is known. The Investigator should further obtain follow-up information no later than 1 month after the gestational period to obtain maternal/fetal/neonatal outcome and any other relevant information (after obtaining consent from the participant). Upon obtaining pregnancy outcome, the Investigator will complete the pregnancy outcome form and submit it to the study contact on the Study Contact Information page ([Section 10.1.1](#)) of this protocol or by fax to the number in the Investigator Site File.

All information related to the pregnancy and its outcome will be assessed for the occurrence of an AE or SAE. Spontaneous abortions and stillbirths will always be reported as SAEs. Should an AE or SAE occur in the participant and the participant decides to continue in the study after permanently discontinuing study intervention, the event will be processed per routine study guidelines. However, if the participant decides not to continue in the study, all AEs and SAEs will be documented and provided directly to the SAE contact on the Study Contact Information page ([Section 10.1.1](#)) of this protocol. Likewise, if the pregnancy results in the birth of a child and an AE or SAE occurs in the child, the data will be documented and provided directly to the SAE contact.

